Step 2. End-User Usability Evaluation. **Study Population.** Our study participants will be young men and transgender women (inclusive of YMSM and YTGW age 18-29 years) who have engaged in recent high-risk sexual behavior with a man. Inclusion criteria. (1) 18-29 years of age (see justification below); (2) assigned male sex at birth of any current gender identification; (3) understand and read English; (4) sexually active and at risk for HIV infection per CDC guidance (e.g., YMSM or YTGW and recent anal sex with men)¹⁰⁷(5) smartphone ownership; and (6) self-report being HIV-negative or unknown status.. Exclusion Criteria. (1) persons who have a known diagnosis of HIV; and (2) persons for whom the investigators determine that participation may be detrimental to the participant or to the study (e.g., severe cognitive deficit).

Justification for Key Inclusion/Exclusion Criteria. The proposed inclusion ages of 18-29 captures the upper range of the greatest increase in new infections,⁵⁴ and the youngest age is the average age when sexual initiation begins^{108, 109} (see Inclusion of Children section). We also carefully considered inclusion of participants who are taking PrEP and will exclude participants who report taking it at baseline. While there is a growing body of literature on poor PrEP adherence,¹¹⁰⁻¹¹² particularly among Blacks and Latinos (NIMHD funding priority) as these are the two racial and ethnic minority groups who are most heavily burdened by HIV,^{4, 6-8, 113} including those on PrEP at baseline would attenuate the intervention effect due to PrEP treatment guidelines, which

include HIV testing at 3-month intervals. We will be collecting data on PrEP use and self-reported adherence to PrEP as part of the trial. Individuals on PrEP at follow-up visits will be encouraged to follow their current treatment protocol with their PrEP provider, including HIV/STI testing requirements and medical visits. We will control for PrEP use at follow-up in all analyses.

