Sample. Our sample will include 525 Black, Latino, and other young men and transgender women (inclusive of YMSM and YTGW aged 18-29 years), with Chicago: N=180 and New York: N =345; representing the population size of each city.¹²⁸ **Statistical power and sample size calculation.** This study will use a 2:2:1 RCT design. We plan to recruit total 525 subjects (210, 210, and 105 will be in arm 1, 2, and 3, respectively). The power and sample size calculations are based on the comparison of HIV testing rates in the mLab App arm compared to the standard of care HIV information control arm for Hypothesis 1 (i.e., compare HIV testing at 6 months and re-testing during 7 to 12 months). We calculated the statistical power to detect a difference across all participants (YMSM and YTGW). Our study is not powered to detect differences in outcomes in YMSM and YTGW separately but we will analyze differences in effect by gender identity (see Data Analysis Section below). The effect size is calculated based on the findings from the FORTH RCT⁷⁵ in which self-testing resulted in a two times increase in frequency of HIV testing in high-risk MSM, and a nearly four times increase in non-recent testers compared with standard care, without reducing the frequency of facility-based HIV testing. Using a Poisson distribution, we estimated a 40% HIV testing rate over 6 months for the control group and approximately 60% HIV testing rate for the intervention group. We are using a more conservative effect size than the one **reported** previously by assuming 60% testing rate for the intervention as compared to 85% in the FORTH RCT study.⁷⁵ This 20% difference is equivalent to a medium effect size. All power calculations are based on alpha=0.05 and two-sided tests of the primary comparison and an attrition rate of 20% at 6 and 12 months. We will have at least 80% power for Hypothesis 1, to conduct two tests simultaneously (i.e., to compare HIV testing rate during the first 6 months and to compare re-testing rate during 7 to 12 months).

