Alternatives and Potential Limitations. Given that participants must be HIV negative to participate in the study, HIV testing will be included as the final screening component to verify study status prior to enrolling. This will help ensure that participants are not falsifying information on their screeners to enroll in the study. Importantly, participants are expected to continue normal healthcare activities during the course of the study and to be offered HIV testing referral information and on-site testing through existing service providers.

Arm 2- Standard of care HIV information control arm. Youth will receive standard-of-care HIV/STI testing-related risk reduction counseling, a box of condoms, PrEP assessment, and referral information for clinics that provide PrEP during your first visit. Youth randomized to arm 2, standard of care control, will be sent an email or text with links to mobile-optimized online prevention information, including PrEP and HIV testing information that is found on the CDC website.¹²⁷ They will also receive a study information card listing the Columbia University School of Nursing / Lurie Children's study teams' contact information. Once youth are randomized, they will be analyzed according to their original assignment (i.e., intent-to-treat).

Arm 3-HIV home testing arm. Youth randomized to arm 3 will be provided with the 2 OraQuick tests (including the package insert), and a box of condoms to take home at baseline. They will receive 2 more OraQuick tests at the 6 month visit. Participants may come in person to receive their tests or their tests may be mailed to them at their verified address if they are unable to complete an in-person 6 month visit. OraQuick tests will be sent via tracked shipping through USPS, FedEx, UPS. At their baseline appointment, youth will also be sent an email or text with links to mobile-optimized online prevention information, including PrEP and HIV testing information that is found on the CDC website. They will also receive a study information card listing the Columbia University School of Nursing / Lurie Children's study teams' contact information

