self-testing) is the proportion of participants who self-report being tested for HIV in the past 6 months. The secondary goal is to collect and analyze data on the app's test interpretation performance. For the intervention arm (arm 1), we will also have data to confirm their self-report since we will have a photo image of their OraQuick test. We will assess and describe any bias in self-report of HIV testing in the intervention condition.

Follow-Up Surveys. All participants will receive a follow-up survey at 6 and 12 months after the baseline visit. The follow-up survey will be administered either in person on an iPad or, if they are unable to complete an in-person visit, remotely through a Qualtrics survey distributed via email. In total there will be three survey time points for all study participants (baseline, 6 and 12 months). Study participants will receive \$40 at baseline, \$55 at 6-month follow up, and \$75 at 12-month follow up for the time to complete the surveys.

Data Analysis. Groups 1, 2, and 3 will be described with respect to baseline characteristics (e.g., means, standard deviations, ranges, and proportions). Before beginning formal analyses, we will examine the patterns of missing data, paying special attention to the balance of missing data in the study arms. From our prior trials, we anticipate all participants will provide baseline data, 90% will provide immediate post-intervention data, and approximately 80% will complete the 6 and 12 month post-enrollment assessment. Analysis of Intervention Effects.

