All multivariate analyses will be preceded by standard descriptive bivariate analyses to describe the key variables and relationships among them. These analyses will include means, frequency tables, histograms, and examination of distributions. Frequencies and rates of HIV tests, as well as corresponding confidence intervals, will be calculated for each arm. All statistical tests will be two-sided tests with the level of significance at 0.05. Hypotheses testing will be based on logistics models to compare (1) HIV testing during the first 6 months; and (2) HIV re-testing at 7-12 months between the mLab App arm and the control (*Hypothesis 1*). We will conduct stratified analyses to examine the differences in testing uptake in subgroups (i.e., racial/ethnic, age, YMSM vs. YTGW, and risk level). Effect sizes will also be compared between arms 1 and 3 to describe differences in testing and linkage behavior attributable to the mLab app with home test distribution versus home test distribution only. Linkage to care will be measured by the percent of study participants who tested positive and

attended a first HIV care appointment at NYP/Columbia or Lurie or who provide documentation of care at another clinic and the time to link to care after positive result. Follow-up surveys for HIV positive participants will also include questions regarding positive diagnosis, such as disclosure and seeking care. For participants who test HIV positive, we will compare the rates of linkage to care between the mLab App arm and the control arm using Fisher's exact test (*Hypothesis 2*). However, because the number of positive (HIV) tests is expected to be approximately 25-40, this part of the study will not have power to detect a significant statistical difference between groups.

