Missing Data. Multiple imputation (MI) methods will be applied to address missing values under the missing at random (MAR) assumption (i.e., missingness can be fully accounted for by variables with complete information).¹⁴¹ These analyses will be complemented with assessment of how sensitive the inferences are to the MAR assumptions. Sensitivity analysis will be performed based on selection models for dropout.¹⁴²⁻¹⁴⁴ Intention-to-Treat (ITT) Analysis: All analyses will use the ITT principle,¹⁴⁵ which requires subjects' data to be analyzed as randomized, regardless of whether they used the mLab App or not.

Aim 3: Monitor and analyze paradata to understand the effect of user engagement of the mLab App on improving HIV testing rates and linkage to care.

To understand barriers and/or facilitators of its use, the mLab app will automatically collect paradata for each user interaction throughout the study. This paradata is considered "free" in that it does not require any additional effort from the user.¹⁴⁶ This data will be analyzed for each user, as well as aggregated to understand what component of the intervention lead to behavior change. We will specifically examine who uses the mLab App and how frequently it is used over time.

Methods. We will capitalize on the use of the extant mLab software which is written as a mobile-friendly web application in hypertext markup language (HTML), hypertext preprocessor (PHP), JavaScript, and Python (for computer vision), and integrates with REDCap for backend data storage. On each page of the mLab app, a PHP script logs every user interaction before the page of the application is displayed to the user. Therefore, any event that would refresh or send the user to a new page (e.g., HTML links) initiates an event-driven paradata capture. The PHP script transmits the data to REDCap through the secure REDCap API.

Data Analysis. The primary paradata that will be collected is shown in Table 4. From this data, we will derive the following use data for each session: duration on each page, page progression through the application, time from login to result, number of rapid test pictures previewed before sent for result, and total time prior to logout. We will analyze the data on multiple scales and perspectives: individual-level (i.e. user-level), application-level, page-level, session-level, and how these differ by demographic characteristics, HIV testing history, technology

Table. Paradata Collected for Each mLab Event

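### Controlling for PrEP use at follow-up in every analysis adjusts the primary comparison for a variable that arises after randomisation

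*Combined protocol and SAP*

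**What the plan says.** The rule is one sentence in the Justification for Key Inclusion/Exclusion Criteria (Aim 1, Step 2): "We will control for PrEP use at follow-up in all analyses". Although it sits under Aim 1, its paragraph discusses the intervention effect, the trial and follow-up visits. Those belong to the randomised trial; Aim 1 usability testing is a single session. The Aim 2 eligibility section carries the Aim 1 criteria into the trial.

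The Aim 2 text that the rule has to fit with is this:

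- **Outcome.** The primary outcome is "the proportion of participants who self-report being tested for HIV in the past 6 months". Any self-reported test counts.
- **Model.** The Data Analysis section says "Hypotheses testing will be based on logistics models to compare (1) HIV testing during the first 6 months", with a second model for re-testing in months 7-12. It lists no covariates and does not say whether the PrEP rule applies.
- **Principle.** The ITT paragraph requires participants' "data to be analyzed as randomized, regardless of whether they used the mLab App or not", and the Arm 2 description says that "they will be analyzed according to their original assignment (i.e., intent-to-treat").
- **Power.** "we estimated a 40% HIV testing rate over 6 months for the control group and approximately 60% HIV testing rate for the intervention group", with "an attrition rate of 20% at 6 and 12 months" and the statement "We will have at least 80% power for Hypothesis 1".

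Current PrEP users are excluded at baseline in both eligibility sections. All three arms receive PrEP assessment, clinic referral and links to PrEP information.

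**The concern.** Because nobody is on PrEP at entry, PrEP use recorded at 6 or 12 months can be affected by the assigned arm. The plan's own reason for excluding PrEP users is that PrEP care brings HIV testing every three months, so the variable is also tied to the outcome. A covariate that may be affected by treatment and that predicts the outcome should not be in a model meant to estimate the total effect of assignment.

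If the app arm takes up more PrEP, testing gained that way is removed from the estimate. If it takes up less, the estimate is inflated and the test can reject when assignment has no total effect. The documents support neither direction firmly. The Aim 1 use cases include PrEP videos in the app, and the app description mentions education on prevention services. Against that, the Background reports a worry that self-testing may reduce contact with providers, where PrEP might be offered. Uptake by arm will not be known until after the model has been fixed.

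**Working it through.** **Inputs from the documents.** Arms 1 and 2 have 210 participants each; attrition is 20%; testing rates are 40% and 60%; the test is two-sided at 0.05.

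**Assumed inputs.** The documents give no PrEP uptake by arm (c0 control, c1 app) and no proportion of PrEP users who test (q). I take q = 95% or 80% and vary uptake.

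**1. The plan's own figure.** Analysed per arm: 210 × 0.8 = 168.

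Power = Φ[(0.20 − 1.96 × √(2 × 0.5 × 0.5/168)) / √((0.24 + 0.24)/168)] = Φ[(0.20 − 1.96 × 0.0546)/0.0535] = Φ(1.74) = 95.9% per test.

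If both tests must succeed and are independent, this is 0.959² = 92.0%. The stated power of at least 80% is reproduced. The unadjusted odds ratio is (0.6/0.4)/(0.4/0.6) = 2.25.

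**2. Adding follow-up PrEP, worked case.** Take c0 = 10%, c1 = 20%, q = 95%, and hold the total effect at 40% versus 60%. Testing among those not on PrEP is then:

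- control: (0.40 − 0.10 × 0.95)/0.90 = 33.9%
- app: (0.60 − 0.20 × 0.95)/0.80 = 51.25%

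A logistic model on the expected cell counts, with arm and PrEP, gives an adjusted odds ratio of 2.003 with standard error 0.239 on the log scale. So z = ln(2.003)/0.239 = 2.905 and power is Φ(2.905 − 1.96) = 83%. The risk difference standardised to pooled PrEP use is 14.8 points, against the true 20.0.

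**3. Other uptake patterns.** The total effect is fixed at 40% versus 60% (odds ratio 2.25).

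| Uptake, control vs app | q | Adjusted OR | Standardised difference | Power |
|---|---|---|---|---|
| 10% vs 10% | 95% | 2.45 | 20.0 points | 97% |
| 10% vs 15% | 95% | 2.22 | 17.5 points | 92% |
| 10% vs 20% | 95% | 2.00 | 14.8 points | 83% |
| 10% vs 30% | 95% | 1.57 | 9.0 points | 44% |
| 10% vs 20% | 80% | 2.05 | 16.7 points | 88% |
| 10% vs 30% | 80% | 1.78 | 13.2 points | 69% |
| 20% vs 10% | 95% | 3.48 | 25.5 points | above 99% |

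For the rows with equal or higher uptake in the app arm, simulation with 10,000 replicates agrees on power to within about one point.

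**4. How large a gap is needed.** With control uptake of 5-15%, single-test power falls below 80% when app-arm uptake is 11-12 points higher (q = 95%) or 15-16 points higher (q = 80%). The plan's 80% refers to two tests together. If both must succeed and are independent, each needs √0.80 = 89.4%, and the gaps shrink to 7-8 points and 9 points.

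**5. False conclusions.**

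- *Effect only through PrEP* (10% vs 20%, q = 95%, equal testing off PrEP): the app arm tests at 0.20 × 0.95 + 0.80 × 0.339 = 46.1% against 40%. The total odds ratio of 1.28 becomes 1.00.
- *No total effect* (40% vs 40%), uptake 20% vs 10%, q = 95%: the adjusted odds ratio is 1.42 and rejection is 28% instead of 5%. With uptake of 10% vs 20% it is 0.70, again with 28% rejection.

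**6. Cases with little or no harm.**

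- Equal uptake: the difference stays at 20.0 points. The move of the odds ratio to 2.45 is non-collapsibility, not bias. Rejection under no effect is 5%.
- PrEP only follows testing (20% of testers and 2% of non-testers start, in both arms): the odds ratio stays at 2.25 and power is 94%, although the standardised difference falls to 18.4 points.

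**The case against.** The strongest reply has four parts.

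- **Wording.** The rule cannot be meant literally, because Hypotheses 2 and 3 use Fisher's exact test and McNemar's test, which take no covariates. The sentence could be a loose remark that the Data Analysis section never adopted. This is fair as to intent. But if the rule binds any named hypothesis test, it binds the Hypothesis 1 logistic models, and nothing in the available text exempts them.
- **Intention to treat.** A covariate moves nobody between arms and excludes nobody for non-use, so the plan's literal definition of ITT is not breached. This stands. The fault is in the estimand: the model estimates an effect with PrEP use held fixed, not the total effect of assignment that was powered.
- **Purpose.** The primary outcome is labelled as uptake of self-testing, so tests driven by PrEP guidelines can be seen as contamination. That is a reasonable secondary question. But the measured outcome is any self-reported test, and excluding PrEP users at baseline already deals with the problem without conditioning on later events.
- **No demonstrated harm.** The documents show no difference in uptake, and all arms get the same PrEP assessment and referral. The 10% vs 30% row needs uptake to triple, and the case with an effect only through PrEP needs home kits and reminders to do nothing by themselves. This is also fair. It limits how likely and how large the harm is, but it is no reason to fix a primary model whose validity depends on uptake being equal.

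**Conclusion.** The concern holds. Followed as written, the plan conditions the primary comparison on a post-randomisation variable that it links to the outcome itself. The estimate is biased for the total effect if assignment changes PrEP uptake, and the bias can run either way. It is negligible if uptake is similar in the two arms. At an app-arm excess of 5 points, single-test power is still about 92%. Falling below 80% takes an excess of roughly 11-16 points for one test, or 7-9 points if both must succeed. All these sizes rest on assumed uptake and on 80-95% of PrEP users testing. The stated sample size and power are not in error. The crude rates by arm that the plan also reports would be unaffected, but the hypothesis test would rest on the adjusted model. This should be fixed before analysis.

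**What to change.** Replace the sentence in the eligibility justification with: *The primary intention-to-treat models for Hypothesis 1 will not adjust for PrEP use at follow-up or any other variable measured after randomisation. PrEP use at 6 and 12 months will be reported by arm. Any model that adjusts for PrEP use at follow-up, and any mediation analysis, will be labelled secondary or exploratory.* Repeat it in the Aim 2 Data Analysis section, next to the logistic models, so that the two places agree.

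The cost is wording in two places. PrEP use at follow-up is already to be collected, the sample size does not change, and the sponsor keeps the PrEP-adjusted analysis under a secondary label.
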